### **5.3 Safety Analysis Set (SAF)**

The Safety Analysis Set (SAF) consists of all randomized subjects who received at least one dose of study drug.

The SAF will be used for summaries of demographic and baseline characteristics and all safety and tolerability related variables.

When the SAF is utilized in an analysis, subjects will be presented by the treatment actually received. Subjects who are randomized to placebo who accidentally receive at least one dose of ASP8062 will be summarized in the ASP8062 treatment group in the SAF.

### **5.4 Pharmacokinetics Analysis Set (PKAS)**

The PKAS will consist of the subset of SAF for which at least one post dose concentration is available.

## **6 ANALYSIS VARIABLES**

### **6.1 Efficacy Endpoints**

The subjects will use a handheld device (an e-diary that will be taken home) to report daily average pain NRS scores, [REDACTED] and to capture rescue medication use. Data will be automatically transmitted to a central database.

The questionnaires on efficacy to be performed during the clinic visits (Fibromyalgia Impact Questionnaire Revised [FIQR], Patient Global Impression of Change [PGIC], Patient Global Impression of Severity [PGIS], [REDACTED]

[REDACTED] nd Hospital Anxiety and Depression Scale [HADS]) depression subscale will be reported on a tablet device that is available at the site. For FIQR, PGIS, [REDACTED], [REDACTED] and HADS, baseline is defined as the last assessment on or prior to the first dose day (Day 1) of double-blind study drug.

#### **6.1.1 Primary Efficacy Endpoint(s)**

The primary efficacy variable is the change from baseline to Week 8 in mean daily average pain score assessed by NRS (0 to 10 scale).

The NRS is a generic instrument for the assessment of pain, consisting of a single question that asks subjects to record their daily average pain on an 11- point scale, where 0 anchors “no pain” and 10 “pain as bad as you can imagine.” The recall period is the last 24 hours.

The subject will use the e-diary to report daily average pain NRS scores from the start of the baseline diary run-in period through Week 10. Subjects will be instructed to complete the NRS in the evening and at a consistent time each day (ideally between 6pm and midnight, however can be captured until 2am the next morning). For this reason, any daily average pain score entered onto the e-diary up to 2am the following day will be attributed to the previous study day in the derivation of the mean daily average NRS pain scores. This is described in more detail in Section 7.11.4.3

Mean daily average NRS pain scores will be derived for each subject as follows:

**Table 3 Derivation of mean daily average NRS pain score**

Analysis Time Point	Derivation
Baseline	Arithmetic mean of non-missing daily pain scores from the last 7 days prior to the randomization visit i.e., using the non-missing scores from Study Days -7 to -1. If the pain score is missing on all of these 7 days, then the score will be set to missing.
Treatment period Week 1, Week 2, Week 3, Week 4, Week 5, Week 6, Week 7, Week 8, EOT	Arithmetic mean of non-missing daily pain scores collected within time window per visit windows defined in Section 7.11.4.3 Table 26. If the pain score is missing on all of the days during the time window, then the score for that time point will be set to missing.
Follow-up period Week 10	

EOT: end of treatment

Change from baseline is defined in Section 7.1. A negative change indicates a reduction/improvement from baseline (i.e., a favorable outcome).

### 6.1.2 Secondary Efficacy Endpoints

Secondary efficacy endpoints include:

- Percentage of subjects achieving  $\geq 30\%$  (or  $\geq 50\%$ ) reduction from baseline to Week 8 in mean daily average pain score assessed by NRS (0 to 10 scale) in the subject’s daily diary.
  - A subject with at least 30% (or 50%) reduction in mean daily average pain score (NRS) from baseline to Week 8 will be classified as a responder; otherwise they will be classified as a non-responder.
  - Subjects who do not have Week 8 data will be classified as non-responders.
  - Subjects who do not have baseline data will be classified as non-responders.
- Percentage of subjects achieving  $\geq 30\%$  (or  $\geq 50\%$ ) reduction from baseline to EOT in mean daily average pain score assessed by NRS (0 to 10 scale) in the subject’s daily diary.

- A subject with at least 30% (or 50%) reduction in mean daily average pain score (NRS) from baseline to EOT will be classified as a responder; otherwise they will be classified as a non-responder.
- Subjects who do not have EOT data will be classified as non-responders.
- Subjects who do not have baseline data will be classified as non-responders.

Percent change from Baseline is defined in Section 7.1 A negative percent change indicates a reduction/improvement from Baseline (i.e., a favorable outcome).

- Change from baseline to Weeks 2, 4, 8 and EOT in the FIQR function, symptoms and overall impact subscales.

The 21-item FIQR contains 3 subscales: function (9 questions), overall impact (2 questions), and symptoms (10 questions). Subjects answer each question on an 11-point NRS, with anchors appropriate to each question on a tablet device during the clinic visit. The recall period is the last 7 days or, for the function subscale, the last time the activity was performed if not within the 7-day recall period.

For each subject the items described in Table 4 will be derived. The questionnaire should be considered to be invalid if three or more of the individual questions are unanswered. In this case, all subscales and the total score would be set to missing, even if a particular subscale has no missing items.

Change from baseline is defined in Section 7.1 A negative change indicates a reduction/improvement from baseline (i.e., a favorable outcome).

**Table 4 Derivation of FIQR Subscales and Total Score**

Analysis Time Point	FIQR Item	Derivation
Baseline, Treatment period Week 2, Week 4, Week 8, EOT,	Function subscale score Rate the difficulty of the following activities: 3) Brush or comb your hair 4) Walk continuously for 20 mins 5) Prepare a homemade meal 6) Vacuum, scrub or sweep floors 7) Lift and carry a full bag of groceries 8) Climb one flight of stairs 9) Change bed sheets 10) Sit in a chair for 45 mins 11) Go shopping for groceries	Sum of scores from questions 1 to 9.  In the case of missing data, unanswered questions should be compensated using the following “weighting” factor: If only x questions from the Function subscale were answered, the added score of the x questions should be weighed by 9/x.  The range of scores will be 0 to 90, with a lower score indicating better (higher) function.
Follow-up period Week 10	Overall impact subscale score:  12) Fibromyalgia prevented me from accomplishing goals for the week 13) I was completely overwhelmed by my fibromyalgia symptoms	Sum of scores from questions 10 and 11.  In the case of missing data, unanswered questions should be compensated using the following “weighting” factor: If only x questions from the Overall impact subscale were answered, the added score of the x questions should be weighed by 2/x.  The range of scores will be 0 to 20, with a lower score indicating better (lower) impact.
	Symptoms subscale score: Please rate: 14) Your level of pain 15) Your level of energy 16) Your level of stiffness 17) The quality of your sleep 18) Your level of depression 19) Your level of memory problems 20) Your level of anxiety 21) Your level of tenderness to touch 22) Your level of balance problems 23) Your level of sensitivity to loud noises, bright lights, odors and colds	Sum of scores from questions 12 to 21.  In the case of missing data, unanswered questions should be compensated using the following “weighting” factor: If only x questions from the Symptoms subscale were answered, the added score of the x questions should be weighed by 10/x.  The range of scores will be 0 to 100, with a lower score indicating a better (lower) level of symptoms.
	Total score	A normalization factor is applied to each of the three subscale scores: the function subscale score is divided by 3, the overall subscale score is divided by 1 (i.e. it is left unchanged), and the symptoms subscale score is divided by 2.  The total FIQR score is the sum of the three normalized subscale scores. The range of scores will be 0 to 100, with a lower score indicating a better response.

EOT: end of treatment

- Overall subject improvement assessed by PGIC at Weeks 2, 4, 8, and EOT.

[figure not shown]
The PGIC is a self-administered 7-point Likert scale that asks subjects to evaluate their fibromyalgia relative to baseline. This is a single question and the grade ranges from 1 to 7, where 1 anchors “Very Much Improved” and 7 anchors “Very Much Worse”. Subjects will complete the questionnaire during the clinic visits on a tablet device.

### 6.1.3

A 2D grayscale heatmap showing a diagonal band of high intensity (white) against a black background. The band is approximately 10 pixels wide and extends from the top-left to the bottom-right. The background is black with some minor noise.

--

*Table continued on next page*

1

1

1

The figure consists of a 3x3 grid of 2D bar charts. Each chart has a vertical axis on the left and a horizontal axis at the bottom. The bars are black and the background is white. The charts are arranged in a 3x3 grid.

- Row 1:** The first chart has a single bar extending to the right. The second chart has a single bar extending to the right. The third chart has a single bar extending to the right.
- Row 2:** The first chart has a single bar extending to the right. The second chart has a single bar extending to the right. The third chart has a single bar extending to the right.
- Row 3:** The first chart has a single bar extending to the right. The second chart has a single bar extending to the right. The third chart has a single bar extending to the right.

A large black rectangular redaction box covers the majority of the page content, from approximately y=111 to y=300. The box is positioned in the center of the page, with a thin white border. The rest of the page is white with minor scanning artifacts.

The table consists of approximately 15 rows and 5 columns. The first column contains the following text:  
1. [REDACTED]  
2. [REDACTED]  
3. [REDACTED]  
4. [REDACTED]  
5. [REDACTED]  
6. [REDACTED]  
7. [REDACTED]  
8. [REDACTED]  
9. [REDACTED]  
10. [REDACTED]  
11. [REDACTED]  
12. [REDACTED]  
13. [REDACTED]  
14. [REDACTED]  
15. [REDACTED]  
The last column contains the following text:  
1. [REDACTED]  
2. [REDACTED]  
3. [REDACTED]  
4. [REDACTED]  
5. [REDACTED]  
6. [REDACTED]  
7. [REDACTED]  
8. [REDACTED]  
9. [REDACTED]  
10. [REDACTED]  
11. [REDACTED]  
12. [REDACTED]  
13. [REDACTED]  
14. [REDACTED]  
15. [REDACTED]  
The middle columns (2-4) are completely redacted with black bars.

[figure not shown]
*Table continued on next page*

[REDACTED]	[REDACTED]	[REDACTED]

[REDACTED]	[REDACTED]	[REDACTED]

Table continued on next page
------------------------------

*Table continued on next page*

The figure consists of a 2x8 grid of black bars on a white background. The top row contains 8 bars, and the bottom row contains 8 bars. The bars are of varying lengths, with some being very short and others extending almost to the top/bottom of the frame. The bars in the top row are positioned such that they overlap the vertical center line, while the bars in the bottom row are positioned such that they do not overlap the vertical center line. The bars are arranged in a staggered pattern across the grid.

## 6.2 Safety Variables

The schedule of safety assessments is shown in Table 1. Baseline is defined as the last assessment on or prior to the first dose day (Day 1) of double-blind study drug.

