## Definition of Key Study Terms

Terms	Definition of terms
Baseline	Assessments of subjects as they enter a trial before they receive any treatment.
Baseline Diary Run-In	7-day period in which subject completes NRS [REDACTED] on handheld device daily beginning at Day -7 through Day -1.
Double-Blind	The study subjects, Investigator(s)/Site staff and Astellas study team will be blinded to treatment.
Early Discontinuation (ED)	The act of concluding participation, prior to completion of all protocol-required elements, in a trial by an enrolled subject. Four categories of discontinuation are distinguished: a) dropout: Active discontinuation by a subject (also a noun referring to such a discontinued subject); b) Investigator-initiated discontinuation (e.g., for cause); c) loss to follow-up: cessation of participation without notice or action by the subject; d) Sponsor-initiated discontinuation. Note that subject discontinuation does not necessarily imply exclusion of subject data from analysis. "Termination" has a history of synonymous use, but is now considered non-standard.
Endpoint	Variable that pertains to the efficacy or safety evaluations of a trial.
Enroll	To register or enter a subject into a clinical trial. NOTE: Once a subject has signed the informed consent, the clinical trial protocol applies to the subject.
End of Study (EOS)	End of study for each subject has occurred when the final protocol-defined assessment has been completed. In this study, the last protocol defined assessment is approximately 4 weeks after last study drug dose.
End of Treatment (EOT)	The date the last dose of study drug was taken by the enrolled subject.
Electronic Patient Reported Outcomes (ePRO)	An electronic patient-reported outcome (ePRO) is a patient-reported outcome that is collected by electronic methods.
Follow-up Period	The weeks following the final dose of study drug for all subjects. This includes a Follow-up visit and an End of Study Phone Call.
Independent Data Monitoring Committee (IDMC)	The Independent Data Monitoring Committee (IDMC) is responsible for the interim futility evaluation of efficacy data defined in the IDMC Charter. Participants in the IDMC include, but may not be limited to: an Independent Astellas Statistician who is not on the study team, and does not communicate with study team or Site staff. The IDMC will evaluate unblinded data and provide conclusion of futility analysis to Astellas Management.

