### **6.2.3 Vital Signs**

Vital signs variables are raw values (i.e., values at each scheduled visit) and changes from baseline in systolic blood pressure (SBP), diastolic blood pressure (DBP) and pulse rate at Day 1 2-hours post dose, Weeks 2, 4, Week 8/EOT and Week 10. Orthostatic SBP, DBP and pulse rate are assessed on Day 1 pre-dose, Day 1 2-hours post dose, Week 8/EOT (triplicate supine measurements approximately 1 minute apart [-3, -2, -1 minutes before standing] followed by a single standing measurement approximately 3 minutes after standing). Single resting measurements of SBP, DBP and pulse rate are measured on at Screening, Weeks 2, 4 and Week 10.

Orthostatic vital signs (SBP, DBP, pulse rate) will be derived for each subject as follows:

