#### **7.5.3 Clinical Laboratory Evaluation**

The baseline visit is the last measurement taken prior to first dose of study drug.

Quantitative clinical laboratory variables, i.e., hematology & coagulation, and biochemistry will be summarized using mean, SD, minimum, maximum and median for each treatment group at each visit. Additionally, a within-subject change will be calculated as the post-baseline measurement minus the baseline measurement and summarized in the same way. Each laboratory result will be classified as low (L), normal (N), or high (H) at each visit according to the laboratory supplied reference ranges.

The number and percentage of subjects below and above the reference range will be summarized for each treatment group at each visit.

For hematology and biochemistry, two types of shift tables will be presented for each treatment group:

- Shift tables of reference range changes from baseline to post-baseline value at each specified time point (low, normal, high), and
- Summary shifts of reference range changes from baseline to post-baseline value at each specified time point (shift from normal or high to low, shift from normal or low to high, categorized increase [shift from low to normal, low to high or from normal to high], categorized no change [value stays in the same reference range], categorized decrease [shift from high to normal, high to low or from normal to low]).

The following list of parameters will be summarized using descriptive statistics and for the shift table.

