### 7.5.4 Vital Signs

The baseline visit is the last measurement taken prior to the first dose of study drug.

Supine (average)/resting vital signs (SBP, DBP and pulse rate) will be summarized using mean, SD, minimum, maximum and median by treatment group and visit (Baseline, Day 1 2-hours post-dose, Week 2, Week 4, Week 8/EOT, Week 10). Additionally, a within-subject change will be calculated per visit as the post-baseline measurement minus the baseline measurement and summarized by treatment group and visit. Section 7.11.5.3 describes the derivation of visit windows for vital signs.

Standing vital signs (SBP, DBP and pulse rate) will be summarized using mean, SD, minimum, maximum and median by treatment group and visit (Baseline, Day 1 2-hours post-dose, Week 8 / EOT). Additionally, a within-subject change will be calculated per visit as the post-baseline measurement minus the baseline measurement and summarized by treatment group and visit.

Table 23 describes PCS criteria for vital signs. The number and percentage of subjects with PCS values in vital signs using the subject's worst value during double-blind treatment period will be presented by each treatment group. The summary will include all vital signs at both scheduled and unscheduled visits. It will include resting and orthostatic (supine [average] and standing) vital signs. For criteria comparing with baseline, vital signs at standing will be compared with vital signs at standing and vital signs at supine (average)/resting will be compared with vital signs at supine (average)/resting.

Another summary will be created using the subject's worst value (resting vital signs only) during the follow-up period.

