**Table 30 Day Windows: Laboratory, Vital Sign Variables and C-SSRS**

Analysis Time Point	Target Day	Visit Window (Day)
Week 2	Study day 15	Study days 2 to 22
Week 4	Study day 29	Study days 23 to 43
Week 8	Study day 57	Study days 44 to 71
EOT a	Not applicable	Study day 2 to Follow-up day 4
Double-blind treatment period b	Not applicable	Study day 2 to Follow-up day 4
Week 10 c	Follow up day 14	Follow-up days 5 to 28
Follow-up period d	Not applicable	Follow-up day 5 onwards

Baseline is defined as the last assessment on or prior to the first dose day (Day 1) of double-blind study drug.

a EOT value is the last available non-missing post-baseline measurement within the visit window. Vital signs will also include Day 1 2 hours post-dose.

bOnly applicable to potentially clinically significant laboratory parameters, potentially clinically significant vital signs, orthostatic outlier vital signs and C-SSRS. Vital signs will also include Day 1 2 hours post-dose.

cOrthostatic vital signs are not captured at Week 10.

dOnly applicable to potentially clinically significant laboratory parameters, potentially clinically significant vital signs and C-SSRS.

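### SAP 6.2 and the Table 30 footnote define the vital-sign baseline by calendar day, which selects the Day 1 two-hour post-dose reading and contradicts SAP 7.5.4

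*SAP*

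**What the plan says.** The SAP gives two baseline rules that both apply to vital signs.

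- **By calendar day.** SAP 6.2, for safety variables in general: "Baseline is defined as the last assessment on or prior to the first dose day (Day 1) of double-blind study drug". The same sentence stands under Table 30 in SAP 7.11.5.3, which gives the analysis windows for laboratory variables, vital signs and the C-SSRS.
- **By dose time.** SAP 7.5.4, for vital signs: "The baseline visit is the last measurement taken prior to the first dose of study drug". SAP 7.5.3 has the same rule for laboratory data ("The baseline visit is the last measurement taken prior to first dose of study drug"), and SAP 7.5.5 has it for ECGs.

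Footnote h of the schedule of assessments, in both documents, puts two orthostatic sets on Day 1, one before dosing and one about two hours after. SAP 7.1 makes Study Day 1 the day of the first dose.

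The SAP otherwise handles the two-hour reading as post-baseline:

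- SAP 6.2.3 plans a change from baseline for "pulse rate at Day 1 2-hours post dose, Weeks 2, 4, Week 8/EOT and Week 10", among other parameters.
- Table 13 lists it under the treatment period.
- SAP 7.5.4 gives the supine/resting visits as "Baseline, Day 1 2-hours post-dose, Week 2, Week 4, Week 8/EOT, Week 10", with baseline and the two-hour visit separate.
- Table 30 footnotes a and b, on the end-of-treatment and double-blind windows, add: "Vital signs will also include Day 1 2 hours post-dose".

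The protocol's key terms define baseline as: "Assessments of subjects as they enter a trial before they receive any treatment".

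**The concern.** The two rules select different records. The latest assessment on Day 1 is the two-hour reading, so a programmer who follows 6.2 or the Table 30 footnote to the letter takes a post-dose value as baseline. Table 30 even contradicts itself: its baseline footnote admits the reading as baseline, while footnotes a and b count it as on-treatment.

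The two-hour set is the only scheduled vital-sign measurement after the first dose on Day 1, and it falls inside the 1.5 to 3 hour range that protocol 1.2 gives for time to peak concentration. Its change from pre-dose is the summary that describes any acute effect. Under the calendar-day rule that change disappears, and every later change is measured from a value taken on drug in the active arm.

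**Working it through.** The plan states no figure to reproduce. The check has three parts.

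**1. Which record each rule selects.** The scheduled vital-sign records up to Week 2 are Screening, Day 1 pre-dose, Day 1 two hours post-dose, and Week 2.

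| Rule | Eligible records | Selected as baseline |
|---|---|---|
| SAP 6.2 and Table 30 footnote (on or before Day 1) | Screening, Day 1 pre-dose, Day 1 two-hour | Day 1 two-hour |
| SAP 7.5.4 (before first dose) | Screening, Day 1 pre-dose | Day 1 pre-dose |

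The duplicate rules in SAP 7.11.5.1 do not restore the pre-dose value. Same-day averaging excludes orthostatic vital signs, which are what is measured on Day 1. For several orthostatic measurements in one window, the later is used.

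**2. Effect on the change summaries.** Write X(pre), X(2h) and X(t) for a subject's pre-dose, two-hour and later values.

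- Two-hour change with X(2h) as baseline: X(2h) − X(2h) = 0.
- Later change: X(t) − X(2h) = [X(t) − X(pre)] − [X(2h) − X(pre)], the intended change minus the subject's own two-hour change.

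With invented systolic values of 130 pre-dose, 118 at two hours and 112 at Week 8, chosen only to show the mechanics, the changes are −12 and −18 under 7.5.4. Under 6.2 they are 0 and −6.

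Counts per arm from SAP 7.5.4, for three parameters (systolic pressure, diastolic pressure, pulse):

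- Supine/resting: two hours and Weeks 2, 4, 8/EOT and 10 = 5 visits × 3 = 15.
- Standing: two hours and Week 8/EOT = 2 visits × 3 = 6.
- Total: 15 + 6 = 21 change summaries.
- Zero by construction: 2 positions × 3 parameters = 6.
- Offset: (4 × 3) + (1 × 3) = 15.

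**3. Effect on Table 23.** That summary counts subjects by their "worst value during double-blind treatment period will be presented by each treatment group".

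| Parameter | Criteria | Using change from baseline |
|---|---|---|
| Systolic pressure | 4 | 2 |
| Diastolic pressure | 4 | 2 |
| Pulse rate | 6 | 4 (two of them combined with an absolute limit) |
| Total | 14 | 8 |

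For those 8, the scheduled double-blind readings that can contribute fall from 4 (two hours, Weeks 2, 4 and 8) to 3 for supine/resting, and from 2 (two hours, Week 8) to 1 for standing. The counts do not become zero, because later visits still contribute. Each later comparison carries the offset from step 2, so a subject may be gained or lost depending on the direction of the two-hour change.

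**The case against.** The strongest reply is that the SAP already settles the matter. SAP 7.5.4 is the section that specifies the vital-sign analysis, while 6.2 is one general sentence for all safety variables. Every list of time points separates the two-hour reading from baseline, and the protocol's key term agrees. The literal reading would also make an expressly planned change zero for everyone, and an all-zero column would probably be noticed at the review of data and tables planned before hard lock. The summaries are descriptive, and SAP 7.5 rules out hypothesis tests on safety parameters. The counts above show how many outputs depend on the baseline definition, not how large an effect is likely.

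Most of this stands. The intent is clear, the harm is conditional, and the counts are not effect sizes. The SAP revision history also supports a pre-dose intent, since version 2.0 added the Table 30 footnote placing the two-hour reading among the collected vital signs. But clear intent elsewhere does not make the written rule correct. Table 30 is the window table for vital signs, so its footnote is a natural place to take the baseline from, and nothing gives 7.5.4 precedence. A zero column is easy to notice, but the offset in the other 15 summaries is not.

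Two limits apply. Laboratory and ECG baselines are unaffected only as scheduled: an unscheduled Day 1 post-dose test or ECG, which the protocol permits, would be caught by the same wording. And the absence of vital-sign findings suggestive of a safety issue in phase 1 (protocol 1.2) is narrower than evidence of no shift at two hours.

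**Conclusion.** The concern holds. SAP 6.2 and the Table 30 footnote are wrong as worded for vital signs and conflict with SAP 7.5.4, with the protocol definition, and with the SAP's own use of the two-hour reading.

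The consequence is conditional on that wording being programmed in place of 7.5.4. In that case 6 of 21 change summaries per arm carry no information, 15 are offset, and the two-hour reading drops out of 8 of the 14 Table 23 criteria. The counts assume the scheduled visits only. The documents give no two-hour values, so no size in mmHg or in subjects is claimed, and nothing here says that a known signal would be hidden.

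Not affected are the absolute limits in Table 23, the Table 24 orthostatic criteria (standing against supine at the same time point) and all efficacy results. This should be corrected, but it does not threaten the trial's main conclusions.

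**What to change.** In SAP 6.2 and in the Table 30 footnote, define baseline as the last non-missing assessment before the first dose of study drug, in line with 7.5.4, so that the Day 1 two-hour reading can never serve as baseline. Use the same wording under Table 31. No post-dose Day 1 ECG is scheduled, so there the change is mainly for consistency. SAP 7.11.5.1 needs no change.

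The cost is a few words in three places. No new data are needed, because the pre-dose and two-hour sets are already separate time points.
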